6.1.8 Renal Transplant Management of Proteinuria

Renal transplant subjects will undergo a urinalysis at each study visit as part of the surveillance for renal injury including renal graft rejection. If new onset or increased proteinuria is identified it is recommended that this be evaluated further and in conjunction with the patient's nephrologist. If further work up confirms a new or increased proteinuria that is considered to be clinically significant, e.g., urine protein/creatinine ratio or 24-hour urine protein > 1 g on two or more occasions, then further evaluation for possible renal graft rejection or HCV associated renal disease is recommended and consideration should be given to the performance of an allograft biopsy with immunofluorescence and electron microscopy per KDIGO Clinical Practice Guidelines. In the setting of confirmed renal rejection, continuation of the study drugs should be per investigator discretion. If the investigator wishes to pursue alternative management of study drugs in the setting of histologically confirmed rejection, then the Primary Therapeutic Area Medical Director should be contacted to obtain approval. Biopsy tissue from the transplanted organ obtained during the trial to evaluate rejection or other pathologic process should be read locally and the result recorded in the subject source documents. Because of the potential impact of discontinuation (or interruption) of study drugs on immunosuppressant levels, if study drugs are discontinued or interrupted, investigators should ensure that a plan for appropriate immunosuppressant dose modification is in place and that this plan is communicated to the subject.

abbvie ABT-493/ABT-530 M13-596 Protocol Amendment 2 EudraCT 2015-005616-14

6.2 **Product Complaint**

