8.1.5.2 Clinical Laboratory Data

Clinical laboratory tests will be summarized at each visit. The baseline value will be the last non-missing measurement prior to the initial dose of study drug. Mean changes from baseline to each post-baseline visit, including Final Treatment Visit, will be summarized descriptively.

Laboratory data values will be categorized as low, normal, or high based on reference ranges of the laboratory used in this study. The number and percent of subjects who experience post-baseline shifts in clinical laboratory values from low/normal to high and high/normal to low based on the normal range will be summarized.

In addition, the number and percentage of subjects with post-baseline values meeting pre-specified criteria for Potentially Clinically Significant (PCS) laboratory values or toxicity grades will be summarized.

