11.3.1 Variables and Criteria Defining Abnormality

Hematology variables include: hematocrit, hemoglobin, red blood cell (RBC) count, white blood cell (WBC) count, neutrophils, bands, lymphocytes, monocytes, basophils, eosinophils, platelet count, reticulocyte count, prothrombin time (PT), international normalized ratio (INR), and activated partial thromboplastin time (aPTT).

Chemistry variables include: blood urea nitrogen (BUN), creatinine, total bilirubin, direct and indirect bilirubin, alanine aminotransferase (ALT), aspartate aminotransferase (AST), alkaline phosphatase, sodium, potassium, calcium, inorganic phosphorus, cholesterol, total protein, glucose, triglycerides, albumin, chloride, bicarbonate, magnesium, total insulin, gamma-glutamyl transferase (GGT), creatinine clearance (calculated using

Cockcroft-Gault), and estimated glomerular filtration rate (eGFR) calculated using the modification of diet in renal disease (MDRD) equation defined below.

Urinalysis variables include: specific gravity, ketones, pH, protein, blood, glucose, urobilinogen, bilirubin, leukocyte esterase, and microscopic (reflexly performed if other variables are abnormal).

Some of the above laboratory variables are calculated by the laboratory vendor including indirect bilirubin, creatinine clearance, and eGFR by MDRD. The central lab calculates eGFR by MDRD using the following equation, where serum creatinine is measured in mg/dL and age is measured in years:

GFR (mL/min/1.73 m²) = $175 \times (\text{Serum Creatinine})^{-1.154} \times (\text{Age})^{-0.203} \times 1.212$ (if Black) × 0.742 (if Female).

The central lab calculates the estimated creatinine clearance (CrCl) based on the following Cockcroft-Gault formula:

CrCl (mL/min) = $[(140 - age) \times (weight in kg) \times (0.85 \text{ if female})]/[serum creatinine (mg/dL) \times 72].$

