11.3.2 Statistical Methods

The baseline value for clinical laboratory tests will be the last non-missing measurement on or before the day of the first dose of study drug. Values on Day 1 must also be before the time of first dose if time is available. The same baseline value will be used for change to Treatment Period visits and change to Post-Treatment Period visits.

Mean changes from baseline to each post-baseline visit, including applicable post-treatment visits, will be summarized. Each protocol-specified laboratory parameter will be summarized with the sample size, baseline mean, visit mean, change from baseline mean, standard deviation, minimum, median, and maximum.

ABT-493/ABT-530

ABT-493/ABT-530 M13-596 – Statistical Analysis Plan Version 1.0 – 27 October 2016

The laboratory parameters defined in Table 8 will be assigned a toxicity grade of 1, 2, 3, or 4. The number and percentage of subjects with a maximum toxicity grade of 1, 2, 3 or 4, will be summarized. The post-baseline value must be in a toxicity grade that is more extreme than the toxicity grade corresponding to the baseline value to be counted. The summary will also include the number and percentage of subjects with a maximum of at least Grade 3 for all laboratory parameters in Table 8. A listing of all relevant laboratory parameters will be provided for each subject who had an increase to Grade 2 or higher for all laboratory variables in Table 8.

Fable 8.Definitions of Toxicity Grades 1, 2, 3, and 4 for Laboratory V	Values
--	--------

Test	Grade 1	Grade 2	Grade 3	Grade 4
ALT/SGPT	$>$ ULN – 3 \times ULN	$> 3 - 5 \times ULN$	> 5 - 20 imes ULN	> 20 imes ULN
AST/SGOT	$>$ ULN – 3 \times ULN	$> 3 - 5 \times ULN$	> 5 - 20 imes ULN	> 20 imes ULN
Alkaline Phosphatase	$>$ ULN – 2.5 \times ULN	$> 2.5 - 5 \times ULN$	> 5 - 20 imes ULN	> 20 imes ULN
Total Bilirubin	$>$ ULN – 1.5 \times ULN	$> 1.5 - 3 \times ULN$	$> 3 - 10 \times ULN$	$> 10 \times ULN$
Hemoglobin	< LLN $-$ 100 g/L	< 100 - 80 g/L	< 80 g/L	
Absolute Neutrophil Count	$<$ LLN $- 1.5 \times 10^9$ /L	$< 1.5 - 1.0 \times 10^9 / L$	$< 1.0 - 0.5 \times 10^9 / L$	$< 0.5 \times 10^{9}/L$
Platelet count	$< LLN - 75.0 \times 10^9 / L$	$<75.0-50.0\times 10^9\!/L$	$< 50.0 - 25.0 \times 10^9 \! / \! L$	$<25.0\times10^9/L$
INR	$> 1 - 1.5 \times ULN$	$> 1.5 - 2.5 \times ULN$	$> 2.5 \times ULN$	
Creatinine clearance	< LLN - 60 mL/min	< 60 - 30 mL/min	< 30 - 15 mL/min	< 15 mL/min

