Creatinine	$>$ ULN – 1.5 \times ULN	$> 1.5 - 3 \times ULN$	$> 3 - 6 \times ULN$	$> 6 \times ULN$
Albumin	< LLN $-$ 30 g/dL	< 30 - 20 g/L	< 20 g/L	

Assessment of Hepatic Laboratory Parameters

The number and percentage of subjects with maximum on-treatment lab values meeting the following criteria will be summarized:

- ALT \geq 3 × ULN and total bilirubin \geq 2 × ULN;
- ALT \ge 3 × ULN and total bilirubin < 2 × ULN;
 - ALT > 5 × ULN and total bilirubin < 2 × ULN;
- ALT < $3 \times$ ULN and total bilirubin $\ge 2 \times$ ULN.

ABT-493/ABT-530 M12 506 Statistic

ABT-493/ABT-530 M13-596 – Statistical Analysis Plan Version 1.0 – 27 October 2016

The maximum ratio relative to the ULN will be used to determine if subjects meet the criteria listed above. The ALT and total bilirubin values do not need to be concurrent in order to meet the defined criteria. For ALT, the post-baseline value must represent an increase from the first nadir (including baseline) to be counted. First nadir is defined as the last value prior to the first increase. For total bilirubin, a subject will be counted if the post-baseline laboratory value meets the above criteria regardless of the baseline laboratory value (i.e., the post-baseline laboratory value does not need to be worse than the baseline laboratory value).

A listing of all ALT, AST, total, indirect and direct bilirubin, ratio of direct to total bilirubin, and alkaline phosphatase values will be provided for each subject who met any of the criteria defined above. The listings will be reviewed to assess bilirubin (e.g., mixed or direct predominance) and temporal relationships for subjects with $ALT \ge 3 \times ULN$ and total bilirubin $\ge 2 \times ULN$.

The number and percentage of subjects with post-baseline values during the Treatment Period meeting the following criteria will be summarized:

- ALT > 5 × ULN and \geq 2 × baseline;
- AST > 5 × ULN and \geq 2 × baseline;
- Total bilirubin $\geq 2.0 \times ULN$ and > baseline.

As noted above, a post-baseline value must be more extreme than the baseline value to be considered. A separate listing will be provided that presents all lab values for the subjects meeting any of these criteria during treatment.

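### SAP 11.3.2 gives urine protein descriptive statistics only: the protocol's shift count is not carried over, and worsening from an abnormal baseline is counted in neither document

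*SAP*

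**What the plan says.** Protocol 6.1.8 states that "Renal transplant subjects will undergo a urinalysis at each study visit as part of the surveillance for renal injury including renal graft rejection". New or increased proteinuria then prompts further evaluation. Its example of a clinically significant finding is "urine protein/creatinine ratio or 24-hour urine protein > 1 g on two or more occasions".

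SAP 11.3.1 includes urine protein among the laboratory variables: "Urinalysis variables include: specific gravity, ketones, pH, protein, blood, glucose, urobilinogen, bilirubin, leukocyte esterase". SAP 11.3.2 then provides three kinds of laboratory analysis:

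- **Descriptive statistics for every parameter.** "Each protocol-specified laboratory parameter will be summarized with the sample size, baseline mean, visit mean, change from baseline mean", followed by standard deviation, minimum, median and maximum.
- **Toxicity grades.** "The laboratory parameters defined in Table 8 will be assigned a toxicity grade of 1, 2, 3, or 4". Subjects are counted by maximum grade, and those who increase to Grade 2 or higher are listed.
- **Hepatic criteria.** "The number and percentage of subjects with maximum on-treatment lab values meeting the following criteria will be summarized". The criteria there, and in the further set that follows, concern ALT, AST and total bilirubin.

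Protocol 8.1.5.2 plans one more analysis. The number and percent of subjects with "post-baseline shifts in clinical laboratory values from low/normal to high and high/normal to low based on the normal range will be summarized". Urinalysis is not excluded.

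**The concern.** Safety is a primary objective, and Protocol 6.1.8 is a dedicated section on proteinuria in renal recipients. The signal it describes is a change within a subject: proteinuria that is new, or proteinuria that has increased. The natural summary is the number of subjects in whom this happened. SAP 11.3.2 instead specifies a per-visit distribution over the whole safety population, with no split by transplant type. SAP 7.0 does split baseline characteristics by transplant type, and SAP 10.6 does so for SVR12.

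The hepatic side is treated differently. The ALT rule in Protocol 6.1.7.1 has a closely matching subject count in SAP 11.3.2 (ALT above 5 × ULN and at least 2 × baseline). Protocol 6.1.8 has no urine-protein counterpart. If the SAP is programmed as section 11.3 stands, the report could omit how many renal recipients developed new or increased proteinuria, although urine protein is measured repeatedly.

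**Working it through.** The documents state no figure on this point, so there is none to reproduce. The check is a trace of urine protein through every subject-level laboratory count.

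| Count | Source | Covers | Urine protein? |
|---|---|---|---|
| Maximum toxicity grade and Grade 2+ listing | SAP 11.3.2, Table 8 | ALT, AST, alkaline phosphatase, total bilirubin, hemoglobin, neutrophils, platelets, INR, creatinine clearance, creatinine, albumin (11) | No |
| Hepatic criteria | SAP 11.3.2 | ALT, AST, total bilirubin | No |
| Low/normal to high, high/normal to low | Protocol 8.1.5.2 | Clinical laboratory values in general | Yes, if a reference range exists |

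**Status of the third row.** SAP 3.0 says the SAP elaborates the protocol's methods and guides programming. SAP 6.2 contains a same-day rule for summaries of shifts, so such tables were expected. SAP 11.3.2 specifies none. SAP 12.1 lists only resistance and efficacy-subgroup changes. The shift count is therefore neither implemented nor withdrawn. This affects all laboratory parameters; urine protein stands out because it has no Table 8 row to fall back on.

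**What that row would catch.** A subject who is normal at baseline and later high is counted. A subject already high at baseline cannot make a low/normal-to-high move, however much the value rises. None of the laboratory exclusions in Protocol 5.2.2, criterion 9, concerns urine protein, so such subjects can enrol. The increased half of the protocol's signal thus falls in no laboratory count in either document.

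**Illustration only; the inputs are assumed.** Take 15 renal subjects of 90 in total. Suppose *k* renal subjects each rise by 2 units on a numerically coded scale and nobody else changes.

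- Pooled mean change = 2*k*/90.
- Count among renal recipients = *k*/15, with Wilson 95% limits (p + z²/2n ± z√[p(1−p)/n + z²/4n²]) / (1 + z²/n), where n = 15 and z = 1.96.

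| *k* | Pooled mean change | Median change | Maximum change | Renal count (Wilson 95% CI) |
|---|---|---|---|---|
| 1 | 2/90 = 0.02 | 0 | +2 | 1/15 = 6.7% (1.2% to 29.8%) |
| 3 | 6/90 = 0.07 | 0 | +2 | 3/15 = 20.0% (7.0% to 45.2%) |
| 5 | 10/90 = 0.11 | 0 | +2 | 5/15 = 33.3% (15.2% to 58.3%) |

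Reading the minimum and maximum as those of the change, the planned table does reveal that someone rose by 2. It does not report how many subjects did, or in which transplant group. Only the last column does.

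**The case against.** The other side has real points.

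- **The protocol count still stands.** A reader might infer that new proteinuria would appear in no laboratory count at all. The documents do not support that: Protocol 8.1.5.2 has not been withdrawn and SAP 6.2 presumes shift summaries. What can be said is that SAP 11.3 defines no count that includes urine protein. This objection does not reach worsening from an abnormal baseline.
- **Urine protein is not the only renal measure.** Protocol 6.1.8 calls urinalysis part of the surveillance. Creatinine and creatinine clearance are graded per subject in Table 8, and eGFR is summarized. A reader might infer that renal graft safety goes unanalysed; it does not. These measures nevertheless do not report proteinuria, which Protocol 6.1.8 singles out.
- **Adverse-event reporting is a second route.** Protocol 6.1.1.1 makes a laboratory abnormality an adverse event if it leads to discontinuation, needs therapeutic intervention, meets protocol-specific criteria or is considered one by the investigator. Protocol 5.4.1 captures treatment of rejection. Treated rejection is therefore recorded. The protocol-specific limb points to section 6.1.7, not 6.1.8, so untreated proteinuria depends largely on the investigator's judgment.
- **The mean may be a proper summary.** A reader might infer that the mean is invalid because urinalysis protein is an ordered category. The documents do not state the reporting scale. If it is quantitative, the mean is legitimate, though it still counts no cases.
- **A urinalysis table would not measure the protocol's example criterion.** Protein/creatinine ratio and 24-hour protein are not in the routine panel (Protocol Table 2). That is true; the table would describe the scheduled screening measure, not that criterion.

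**Conclusion.** The point holds in a limited form. Urine protein is in none of the 11 Table 8 parameters and none of the hepatic criteria, and SAP 11.3.2 gives it distributional summaries only. The protocol count that could capture new proteinuria is left unspecified in the SAP without a declared change. Increased proteinuria from an abnormal baseline has no laboratory count anywhere. The consequence is incomplete safety reporting in a group of at least 15 renal recipients; the primary efficacy analysis is unaffected.

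No incidence of missed cases can be derived from the documents, and the table of assumed rises is not evidence of one. The conclusion that the protocol's shift count would cover new proteinuria assumes that the laboratory supplies a reference range for urine protein. The conclusion about worsening from an abnormal baseline does not depend on the reporting scale.

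**What to change.** 1. In SAP 11.3.2, specify the Protocol 8.1.5.2 shift table for all laboratory parameters, or declare and justify its removal in SAP 12.1. Restoring it is preferable, since SAP 6.2 already carries the handling rule.
2. For urine protein, add a table of baseline against worst post-baseline value on the laboratory's reported scale (categories if semi-quantitative). Count new and increased proteinuria separately, overall and by transplant type. State the scale and how normal and abnormal are defined on it.
3. Add a by-subject listing of those counted, with concurrent creatinine and eGFR.

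Beyond restoring the promised shift table, the cost is one extra table and one listing from data already collected. It requires SAP wording and programming only, with no new sampling and no change to clinical management. The renal denominators will be small and the percentages imprecise, so the listing should be read alongside the counts.

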discontinuation. One subject with history of irritable bowel disease discontinued for Grade 2 AE of abdominal pain assessed as having a reasonable possibility of relatedness to both the DAAs and RBV. The abdominal pain for this subject resolved after discontinuation from study drugs. The other subject discontinued for the aforementioned Grade 4 SAE of B-cell lymphoma for the purposes of initiating chemotherapy.

In both Studies M14-867 and M14-868, in all subjects with baseline ALT elevations, the ALT levels showed a trend toward normal or became normal with DAA treatment, and there have been no on-treatment ALT elevations above baseline. Other laboratory abnormalities were infrequent and were primarily associated with well-described hemolytic effect of RBV, manifesting as Grade 1 anemia in a total of 4 subjects, all occurring in the RBV-containing arms Study M14-868. Observed total bilirubin elevations were Grade 1 or 2 with predominantly indirect fraction, were mostly isolated occurrences, and normalized or stabilized with continued DAA therapy. Total bilirubin elevations were primarily observed in the RBV-containing arms.

In Part 2 of Study M14-867, ¹⁸ a total of 34 GT1-infected subjects without cirrhosis received ABT-493 and ABT-530 for 8 weeks. Among enrolled subjects, there are 29 treatment-naïve subjects. Thirty-three of the 34 (97%) subjects achieved SVR₁₂. One subject discontinued from study drug due to the non-DAA related SAE of adenocarcinoma but did achieve SVR₄; the subject subsequently died due to the aforementioned SAE prior to the post-treatment Week 12 visit. There have been no other SAEs, discontinuations due to adverse events or deaths. Adverse events have been mostly Grade 1 or Grade 2, with the most frequently reported adverse events being fatigue, diarrhea and nausea. There have been no on-treatment ALT elevations above baseline. This study also contains arms to evaluate genotypes 4-6 (total 34 patients), who received ABT-493 and ABT-530 for 12 weeks, and have achieved SVR₄ of 100%.

[figure not shown]
DDI STUDIES WITH CYCLOSPORINE AND TACROLIMUS

Phase 1 drug-drug interaction studies of ABT-493/ABT-530 have been conducted with tacrolimus and cyclosporine (CsA) in healthy volunteers. The pharmacokinetic results from these studies are summarized below:

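### SAP 11.3.2: a subject with total bilirubin >= 2 × ULN whose ALT is >= 3 × ULN only while falling from a raised baseline fits no row of the paired ALT/bilirubin table

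*SAP*

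**What the plan says.** SAP 11.3.2, under the assessment of hepatic laboratory parameters, lists four criteria (all × ULN): ALT >= 3 with total bilirubin >= 2; ALT >= 3 with bilirubin < 2; nested within that, ALT > 5 with bilirubin < 2; and ALT < 3 with bilirubin >= 2.

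The rules for applying them are:

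- Value used: "The number and percentage of subjects with maximum on-treatment lab values meeting the following criteria will be summarized". Then: "The maximum ratio relative to the ULN will be used to determine if subjects meet the criteria listed above". No criterion is exempted.
- ALT: "For ALT, the post-baseline value must represent an increase from the first nadir (including baseline) to be counted". And: "First nadir is defined as the last value prior to the first increase".
- Bilirubin: "For total bilirubin, a subject will be counted if the post-baseline laboratory value meets the above criteria regardless of the baseline laboratory value".
- Timing: "The ALT and total bilirubin values do not need to be concurrent in order to meet the defined criteria".
- Listing: "A listing of all ALT, AST, total, indirect and direct bilirubin, ratio of direct to total bilirubin" and alkaline phosphatase is promised only for subjects who met at least one of the four criteria.

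The same section has a second summary. It includes total bilirubin >= 2.0 × ULN and above baseline, with a listing of all laboratory values for subjects who meet any of its criteria. Table 8 grades bilirubin separately, and subjects who increase to Grade 2 or higher are listed.

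**The concern.** The first and last criteria look as if they divide subjects with on-treatment bilirubin >= 2 × ULN by whether ALT was also raised. They do so only if every such subject either has a counted ALT >= 3 × ULN or has a maximum ALT below 3 × ULN. An ALT of 3 × ULN or more that is still falling from baseline does neither. It is not counted as a rise, yet it keeps the maximum at or above 3.

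That ALT course is ordinary in this trial. Exclusion Criterion 9 sets the ALT/AST limit at 10 × ULN. Appendix C draws chemistry at Day 3 and Week 1, when a raised ALT may still be on its way down. Protocol section 3.0 reports for Phase 2b that "in all subjects with baseline ALT elevations, the ALT levels showed a trend toward normal or became normal with DAA treatment".

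At stake is an under-count of raised bilirubin in this paired table and its listing. The count would also depend on how a programmer resolves the wording.

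**Working it through.** There is no stated figure to reproduce. The check applies the rules to example ALT courses and then sizes the result.

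**Step 1: classify courses.** Maximum total bilirubin is taken as 2.5 × ULN. ALT is in × ULN with baseline first. First row means ALT >= 3 with bilirubin >= 2; last row means ALT < 3 with bilirubin >= 2. Four readings are used:

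- A: on-treatment maximum for the last row, counted post-nadir ALT for the other rows.
- B: nadir rule for every row.
- C: ALT < 3 means no counted ALT >= 3.
- D: on-treatment maximum only, nadir rule ignored.

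| ALT course | Max on treatment | Max counted | A | B | C | D |
|---|---|---|---|---|---|---|
| 8, 6, 4, 3.2, 2, 1, 0.8 | 6 | none | no row | no row | last | first |
| 8, 5, 2, 2.2, 1 | 5 | 2.2 | no row | last | last | first |
| 8, 2.5, 2, 1 | 2.5 | none | last | no row | last | last |
| 0.8, 0.8, 0.8 | 0.8 | none | last | no row | last | last |
| 8, 5, 2, 3.5 | 5 | 3.5 | first | first | first | first |

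In the top course ALT never increases, so there is no first nadir and nothing can be counted, while the maximum of 6 rules out the last row. Both readings that keep the nadir rule and add no new definition, A and B, leave this subject out. C and D place the subject, but C sets aside the maximum rule for the last row, and D drops the nadir rule.

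A high baseline alone is not enough under A. The third course is already below 3 × ULN at its first on-treatment value and goes to the last row.

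**Step 2: how often such an ALT course arises, under reading A.** Assumptions, none of them from the documents: exponential fall to 0.6 × ULN, half-life 5 to 10 days, within-subject CV 10 to 15%, first on-treatment sample three days after baseline, then Weeks 1, 2, 4, 6, 8 and 12. By simulation, the probability of an on-treatment ALT >= 3 × ULN with no counted ALT >= 3 × ULN is:

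- entry at 5 to 10 × ULN: 0.66 to 0.997;
- entry at 4 × ULN: about 0.29 to 0.74.

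The half-life matters. At 3 days the probability is about 25 to 32% for entry at 5 × ULN and under 4% for entry at 4 × ULN.

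**Step 3: number of subjects.** The share entering at >= 5 × ULN is not given; assume 5 to 15%. The chance of on-treatment bilirubin >= 2 × ULN is not given either; assume 1 to 5%.

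- Entering at >= 5 × ULN: 90 × 0.05 = 4.5 to 90 × 0.15 = 13.5.
- With an unplaceable ALT course: 4.5 × 0.66 = 3.0 to 13.5 × 1.0 = 13.5.
- Also with bilirubin >= 2 × ULN: 3.0 × 0.01 = 0.03 to 13.5 × 0.05 = 0.68.

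Subjects entering between 3 and 5 × ULN would add a little.

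**Step 4: what the other outputs catch.**

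- Bilirubin >= 2 × ULN and above baseline meets the second summary, so it is counted and listed with all laboratory values, ALT included. If it also moves to a worse grade, it enters the Table 8 listing (Grade 2 is above 1.5 up to 3 × ULN).
- Bilirubin >= 2 × ULN but not above baseline fails the second summary. It is no grade increase either, so bilirubin does not trigger the Table 8 listing. Such subjects can be enrolled, since Exclusion Criterion 9 caps direct bilirubin and not total.

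**The case against.** The strongest reply is that this is loose wording with an obvious reading: the nadir rule decides which ALT values count, and a subject with none at or above 3 × ULN is treated as below 3. That is reading C, it leaves no gap, and a sensible programmer may adopt it. It is a fair account of the likely intent. But the SAP does not state it, and it conflicts with the instruction to judge every criterion on the maximum ratio.

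A second reply is that the SAP never promises that the criteria divide up all subjects, and one row is nested in another. That is true. However, the bilirubin rule says a qualifying value is counted regardless of baseline, and here it is not.

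Three stronger readings are tempting, and the documents do not support them:

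- A reader might infer that the SAP confines the nadir rule to the ALT >= 3 rows. It does not say so. The gap does not depend on that split, since a steadily falling ALT fits no row under B either.
- A reader might infer that combined ALT and bilirubin rises are lost from the main liver-injury table. The SAP does not give the table that status. A counted ALT rise to >= 3 × ULN with bilirubin >= 2 × ULN stays in the first row under every reading.
- A reader might take the 4.5 to 13.5 subjects in Step 3 as the number lost. That is only an assumed entry share. Protocol section 3.0 describes Phase 2b bilirubin elevations as Grade 1 or 2, mostly isolated, and mainly in ribavirin-containing arms. The regimen here has no ribavirin.

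**Conclusion.** The point holds as a minor defect. As written, the maximum rule and the first-nadir rule leave some subjects with on-treatment total bilirubin >= 2 × ULN in no row and out of the linked listing. It requires at least one on-treatment ALT >= 3 × ULN, no counted ALT >= 3 × ULN, and bilirubin >= 2 × ULN at some on-treatment visit.

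The probable number is zero or one subject. This rests on the assumed entry share, ALT half-life and bilirubin frequency above; that the gap exists rests only on the SAP's wording. The effect is confined to one descriptive safety table and its listing, and the SVR12 analysis is untouched. A bilirubin rise above baseline remains visible elsewhere, though not paired with ALT in a count. The remaining loss is bilirubin >= 2 × ULN that does not exceed baseline, which the other bilirubin criteria also miss.

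**What to change.** Define and label the last row as total bilirubin >= 2 × ULN and no ALT >= 3 × ULN that counts under the nadir rule. The first and last rows then add up to all subjects with on-treatment total bilirubin >= 2 × ULN. Extend the linked listing to all of those subjects.

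The downside is that the last row will include some subjects whose raw on-treatment ALT was >= 3 × ULN while falling, so the label or a footnote must say so. The cost is one SAP sentence, a footnote and a small programming change. No new data are needed.
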